9.4 Statistical Analyses

In general, continuous variables will be summarized using number (n), mean, median, standard deviation, minimum, and maximum. Time-to-event data will be summarized based on Kaplan-Meier estimates, including but not limited to median (and 95% CI), frequency of participants with events, at risk, rate (and 95% CI) at predefined timepoints. Categorical variables will be summarized using frequency counts and percentages. Proportions are calculated based on the number of participants in the analysis set of interest, unless otherwise specified in the Integrated Analysis Plan. If not explicitly stated, no imputation is used in the analyses.

9.4.1 Efficacy Analyses

All analyses on efficacy endpoints are primarily done on the FAS/SAF.

Reference #	Category	Statistical Analysis
Secondary		
3 – Objective Response	Main	
Objective response rate (ORR), defined as the number of participants having reached a best overall response (BOR) of CR or PR will be calculated along with the corresponding 2-sided exact Clopper-Pearson 95% CI per treatment group.
 
Further details will be provided in the Integrated Analysis Plan.

4 – PFS	Main	
PFS is defined as the time from date of the first treatment until date of the first documentation of PD or death due to any cause, whichever occurs first.

5 – LRC		
LRC is defined as the time from date of the first treatment until date of the first occurrence of progression at the site of the primary tumor or the locoregional lymph nodes.

6 - Time to subsequent cancer treatments		
Time to subsequent systemic cancer treatments is defined as time from date of the first treatment administration until the start date of the first subsequent systemic cancer treatment for SCCHN.
 
Evaluations of tumor response are based on either according to RECIST v1.1 or based on clinical assessment (radiological or clinical, as assessed by Investigator).
 
Kaplan-Meier estimates (product-limit estimates) will be presented together with a summary of associated statistics (median, survival time, and survival rate estimates at 3 and 6 months and every 6 months thereafter if applicable) including the corresponding 2-sided CIs.
 
Further details will be provided in the Integrated Analysis Plan.

BOR=best overall response, CI=confidence interval, CR=complete response, LRC=Local-regional control, OR=overall response, ORR=overall response rate, PD=progressive disease, PFS=progression-free survival, PR=partial response, RECIST=Response Evaluation Criteria in Solid Tumor, SCCHN=squamous cell carcinoma of the head and neck.

9.4.2 Safety Analyses

All safety analyses will be performed on the FAS/SAF except for the analysis of the primary endpoint, which will be performed on the DLT analysis set.

Reference #	Statistical Analysis
Primary	
1 – Occurrence of DLT-like events	
DLT-like events are defined in Section 8.2.5.1.
 
All DLT-like events that occurred in the analysis population during the DLT-like assessment period of each participant will be analyzed.
 
The number and proportion of participants experiencing DLT-like events in the analysis population will be reported together with the corresponding Clopper-Pearson 95% CI.

Secondary	
2 – safety	
TEAEs are defined as AEs emerging or worsening after start of treatment until 30 days after end of treatment. Adverse events will be coded according to the latest available version of the Medical Dictionary for Regulatory Activities (MedDRA). Severity of AEs will be graded by the Investigator using the NCI-CTCAE (Version 5) toxicity grades. TRAEs will be defined as any AE considered as related to study treatment. Incidence of TEAEs which includes AESIs and TRAEs summarized by SOC and PT.

Reference #	Statistical Analysis
	
Laboratory results will also be classified by Grade according to NCI-CTCAE. Worst on treatment grades as well as shifts to worst on treatment grades will be summarized. Measurements without NCI-CTCAE grading will be summarized by above, within, and below normal limits.
 
Vital parameters, weight, and ECOG performance status and corresponding changes from baseline will be presented as descriptive statistics by timepoint.
 
Further details will be provided in the Integrated Analysis Plan.

AE=adverse event, AESI=adverse events of special interest, CI=confidence interval, ECOG=Eastern Cooperative Oncology Group, MedDRA=Medical Dictionary for Regulatory Activities, NCI-CTCAE=National Cancer Institute Common Terminology Criteria for Adverse Events, PT=Preferred Term, SOC=System organ class, TEAE=treatment-emergent adverse event, TRAE=treatment-related adverse event.

9.4.3 Other Analyses

Details on the analyses of plasma concentrations of xevinapant (including metabolite[s], such as D-1143-MET1) during the treatment period will be in the IAP that will be finalized before database lock.

9.4.4 Sequence of Analyses

The sequence of planned analyses is as shown in [Table 17](#).

Additional analysis during the study might be conducted, e.g. for publication or decision making purposes. More details will be described in the IAP and SMC Charter.

Table 17 Sequence of Planned Analysis

	Analysis
SMC	The SMC will review available data during study conduct. The cutoff for the SMC reviews will be triggered when 6, 12, and 18 participants have been treated for at least 5 weeks (DLT-like assessment period) or have experienced a DLT-like event. Additional SMC reviews may be requested by the Sponsor or the SMC.
Primary analysis	The cutoff will be triggered when at least 38 participants meet at least 1 of the following criteria: 
 • Experience at least 1 DLT-like event, regardless of the administered amount of study intervention/completion in the DLT-like assessment period. • Receive at least 60% of the planned cumulative dose of xevinapant and cisplatin during the DLT-like assessment period and either complete the DLT-like assessment period or discontinue study.
Follow-up analysis	Follow-up analyses to report further efficacy and safety data will be done once the End of Study has been reached as defined in Section 4.4 .

DLT=dose-limiting toxicity, SMC=Safety Monitoring Committee.

10

References

Elad S. The MASCC/ISOO Mucositis Guidelines 2019 Update: introduction to the first set of articles. *Support Care Cancer.* 2019;27:3929-31.

Appendix 1 Abbreviations

ADR	adverse drug reaction
AE	adverse event
AESI	adverse events of special interest
AJCC	American Joint Committee on Cancer
AxMP	auxiliary medicinal product
ALP	alkaline phosphatase
ALT	alanine aminotransferase
AML	acute myeloid leukemia
ANC	absolute neutrophil count
AST	aspartate aminotransferase
AUC	area under the curve
BOR	best overall response
CDMO	Contract Development Manufacturing Organization
CIOMS	Council for International Organizations of Medical Sciences
CKD-EPI	Chronic Kidney Disease Epidemiology Collaboration
COVID-19	Corona virus disease-19
CR	complete response
CrCL	creatinine clearance
CRF	case report form
CRO	clinical research organization
CRR	complete response rate
CRT	chemoradiotherapy
CSR	clinical study report
CT	clinical trials, computed tomography
CTA	clinical trial application
CTCAE	Common Terminology Criteria for Adverse Events
DDI	drug-drug interactions
DILI	drug-induced liver injury
DLT	dose-limiting toxicity
DMC	Data Monitoring Committee
DRE	disease-related events
EAC	Endpoint Adjudication Committee

ECG	Electrocardiogram
ECOG	Eastern Cooperative Oncology Group
eCRF	electronic case report form
EDC	electronic data capture
eGFR	estimated glomerular filtration rate
END	elective neck dissection
EOT	end of treatment
ESMO	European Society for Medical Oncology
ER	emergency room
¹⁸ F-FDG	¹⁸ F-Fluorodeoxyglucose
FAS	full analysis set
FFPE	formalin-fixed paraffin-embedded
FU	follow-up
GCP	Good Clinical Practice
G-CSF	granulocyte-colony stimulating factors
GI	Gastrointestinal
GMP	Good Manufacturing Practice
HBcAb	hepatitis B core antibody
HBsAg	hepatitis B surface antigen
HBV	hepatitis B virus
hCG	human Chorionic Gonadotropin
HCP	healthcare provider
HCV	hepatitis C virus
HIV	human immunodeficiency virus
HPV	human papillomavirus
IAP	integrated analysis plan or inhibitor of apoptosis proteins
IB	Investigator's Brochure
ICF	informed consent form
ICH	International Council for Harmonization
IDMC	Independent data monitoring committee
IEC	Independent Ethics Committee
IHC	immunohistochemistry
IMP	investigational medicinal product
IMRT	intensity-modulated radiation therapy

IND	investigational new drug
INR	international normalized ratio
IRB	Institutional Review Board
IRC	Independent Review Committee
IRT	interactive response technology
IVDR	In Vitro Diagnostic Medical Device Regulation
LA SCCHN	locally advanced squamous cell carcinoma of the head and neck
LRC	locoregional control
MASCC	Multinational Association of Supportive Care in Cancer
MRI	magnetic resonance imaging
MTD	maximum tolerated dose
NCCN	National Comprehensive Cancer Network
NCI-CTCAE	National Cancer Institute Common Terminology Criteria for Adverse Events
NIMP	noninvestigational medicinal product
OPC	oropharyngeal cancer
OR	objective response
ORR	objective response rate
OS	overall survival
PCR	polymerase chain reaction
PD	pharmacodynamic, progressive disease
PET	positron emission tomography
PFS	progression-free survival
P-gp	permeability glycoprotein
PK	Pharmacokinetic
POCBP	Person of Childbearing Potential
PR	partial response
PS	performance status
PT	preferred term
PTV	planning target volume
QTcF	corrected QT interval by Fridericia' formula
QTL	quality tolerance limit
QW	Weekly
Q3W	every 3 weeks
RECIST	Response Evaluation Criteria in Solid Tumor

RT	Radiotherapy
RT-QA	RadioTherapy Quality Assurance
SAE	serious adverse event
SAF	Safety
SCCHN	squamous cell carcinoma of the head and neck
SCR	Screening
SDV	source data verification
SMC	Safety Monitoring Committee
SoA	schedule of activities
SoC	standard of care
SOC	system organ class
SUSAR	suspected unexpected serious adverse reaction
TEAE	treatment-emergent adverse event
TRAЕ	treatment-related adverse event
ULN	upper limit of normal

Appendix 2 Response Evaluation Criteria in Solid Tumors (RECIST) V1.1 Applied to This Study in Locally Advanced SCCHN

The text below was derived from [Eisenhauer 2009](#) and [Schwartz 2016](#). Guidance, adjustments and clarification specific to this study in locally advanced SCCHN, and not necessarily in the original articles, has been added.

Background and Definitions

Response and progression will be evaluated in this study based on the international criteria proposed by the RECIST Working Group (Version 1.1). Unidimensional measurements of tumor lesions are used in the RECIST criteria. Individual lesions are either measurable or non-measurable using the criteria provided below.

Study-permitted Imaging Modalities and Associated Procedures

- *CT, MRI*

CT is the best and most reproducible method currently available to measure lesions selected for response assessment. If CT scans have a slice thickness greater than 5 mm, the minimum size for a measurable lesion should be twice the slice thickness. MRI is also acceptable in this study, except for chest imaging, where CT is mandatory.

- *Ultrasound*

Ultrasound is not useful in assessment of lesion size and should not be used as a method of measurement. Needle localization images for biopsy site may however be useful.

- *Endoscopy, laparoscopy*

The utilization of these techniques alone for objective tumor evaluation is not permitted in this study. In this study, biopsy (endoscopic or otherwise) of a suspected new lesion to confirm or exclude malignant nature and provide relevant histological information is strongly encouraged when clinically feasible. Unbiopsied apparent recurrences visible only on endoscopy are not considered sufficient evidence alone to be markers of progression.

- *Tumor markers*

Tumor markers for progression are not used in this study.

- *Cytology, histology*

In this study, biopsy of a suspected new lesion or residual/recurrent mass to confirm or exclude malignant nature and provide histological information relevant to the endpoint is strongly encouraged when clinically feasible.

- *¹⁸F-FDG -PET + CT*

This study incorporates ¹⁸F-FDG -PET scanning to complement CT/MRI scans in assessment of progression (particularly possible 'new' disease.) However, the use of ¹⁸F-FDG-PET to upgrade response to CR unsupported by biopsy is not applied to this study.

Assessment Methodology

- *Assessment methodology of measurable lesions selected for measurement*

Non-nodal tumor lesions must be accurately measured in 1 dimension, the longest diameter in the plane of measurement, with a minimum size of 10 mm by CT scan (irrespective of scanner type) and MRI (no less than double the slice thickness and a minimum of 10 mm). Clinical observations, clinical caliper measurements, photographic assessments, and plain radiographs are not permitted in this study. All measurements should be recorded in metric notation.

The short axis of a lymph node, or conjoined mass of nodes, is the longest perpendicular to the longest diameter in the axial plane. To be considered pathologically enlarged and measurable at baseline, a lymph node must be ≥ 15 mm in short axis when assessed by CT or MRI scan (Scan slice thickness recommended to be no greater than 5 mm). At Baseline and in follow-up, only the short axis of nodes will be measured and followed.

- *Assessment methodology of nonmeasurable disease*

All other lesions (or sites of disease), including small lesions (< 10 mm using spiral CT or MRI scan), as well as measurable lesions that are not selected as target lesions, are considered non-target disease. RECIST criteria define many baseline types of lesion that are always non-measurable, but all of these are excluded from this study. Participants with only non-measurable disease at baseline but whose overall disease burden is still assessable by imaging are considered to have evaluable (non-measurable) disease.

- *Assessment of special lesion types*

- a) *Bone lesions.* There will be no malignant bone lesions at baseline in this study due to inclusion/exclusion criteria, hence discussion of measurability of bone lesions at baseline and of lesions seen at baseline on bone scans is unnecessary.
- b) *Cystic lesions.* Radiographically defined simple cysts should not be considered as malignant lesions. Complex malignant cystic lesions will not occur at baseline in this study due to inclusion/exclusion criteria and hence need not be considered further.
- c) *Lesions with local irradiation:* In this study, all lesions seen at baseline will receive irradiation as part of the study treatment, and therefore it is impossible to avoid radiation impact on assessments. As a result, the processes of selection and following of target lesions should not be influenced by past or current irradiation.

Process for Evaluation of Disease at Baseline

All baseline evaluations except ¹⁸F-FDG-PET scan should be performed as close as possible to the treatment start and never more than 4 weeks before the beginning of the treatment. ¹⁸F-FDG-PET scan performed within 4 weeks before ICF signature could be used at baseline evaluation. The same method of assessment and the same technique should be used to characterize each identified and reported lesion at baseline and during follow-up.

- *Target Lesions*

All measurable lesions up to a maximum of 2 lesions per organ and 5 lesions in total, should be identified as **target lesions** and recorded and measured at baseline. Target lesions should be selected on the basis of their size (lesions with the longest diameter), be representative of all involved organs, but also should be those suitable for reproducible repeated measurements.

Lymph nodes: Pathological nodes which are defined as measurable and may be identified as target lesions at baseline must have a short axis of ≥ 15 mm by CT or MRI scan. Only the short axis of these nodes will contribute to the baseline sum of diameters. All other pathological nodes (those with short axis ≥ 10 mm but < 15 mm) should be considered nontarget lesions. Nodes that have a short axis < 10 mm at baseline are considered nonpathological and should not be recorded or followed.

A sum of diameters (longest for nonnodal lesions, short axis for nodal lesions) for all target lesions will be calculated and recorded as the **baseline sum of diameters**. The baseline sum of diameters will be used as reference to further characterize any later objective tumor changes in the measurable dimension of the disease.

- *Nontarget Lesions*

All other lesions (or sites of disease) including pathological lymph nodes should be identified as **nontarget lesions**. Measurements are not required, except short axis of nodes and then only to confirm or exclude pathological enlargement: these lesions should be subsequently assessed all together as complete response, noncomplete response, or progressive disease. Progressive disease has to be unequivocal, and based on the entire nontarget lesion burden, unless there is only 1 nontarget lesion. Multiple nontarget lesions involving the same organ can be a single item on the case record form (e.g. ‘multiple liver metastases’).

Process for Assessment of Disease at Each Timepoint After Baseline

- *Evaluation of Target Lesions*

A new sum of diameters for all target lesions will be calculated and recorded as the **sum of diameters** for that timepoint. This timepoint sum of diameters will be used for comparison with that at baseline and at the timepoint when the sum of diameters is least (the nadir): the details of the outcome of each comparison are shown in [Table 18](#) below.

Table 18 Response Status Definition for Target Lesions at Each Timepoint

Observed disease	Response	Abbreviation
Disappearance of all target lesions except pathological lymph nodes. All pathological nodes (target or nontarget) must have reduction in short axis to < 10 mm.	Complete Response	CR
At least a 30% decrease in the sum of diameters of target lesions, taking as reference the baseline sum of diameters.	Partial Response	PR
At least a 20% increase in the sum of diameters of target lesions, taking as reference the smallest sum on study or at baseline (the nadir.) In addition to the relative increase of 20%, the sum must also demonstrate an absolute increase of at least 5 mm.	Progressive Disease	PD
Neither sufficient shrinkage to qualify for PR nor sufficient increase to qualify for PD, taking as reference the smallest sum of diameters at baseline or on study.	Stable Disease	SD
1 or more target lesions have not been assessed or assessed using a different modality from baseline or nadir, so adequate comparison of the images is impossible.	Not Evaluable	NE

- *Special points*

Lymph nodes. Lymph nodes identified as target lesions should always have the actual short axis measurement recorded even if the nodes regress to below 10 mm on study. This means that, when lymph nodes are included as target lesions, the sum of diameters may not be zero even if CR criteria are met. In order to qualify for CR, each node must achieve a short axis < 10 mm. For PR, SD, and PD, the actual short axis measurement of the nodes also is to be included in the sum of diameters of target lesions.

Target lesions that become 'too small to measure'. While on study, all lesions (nodal and non-nodal) recorded at baseline should have their actual measurements recorded at each subsequent evaluation, even when very small. However, sometimes the radiologist may not feel able to assign an exact measure and may consider them 'too small to measure'. If the lesion is believed to be present and is faintly seen but too small to measure, a default value of 5 mm should be assigned.

Lesions that split or coalesce on treatment. When non-nodal lesions 'fragment', the longest diameters of the fragmented portions should be added together to calculate the target lesion sum. Similarly, as lesions coalesce, a plane between them may be maintained that would aid in obtaining maximal diameter measurements of each individual lesion. If the lesions have truly coalesced such that they are no longer separable, the vector of the longest diameter in this instance should be the maximal longest diameter for the 'coalesced lesion'.

Target lesions that are biopsied or excised: On occasion, target lesions may be biopsied or excised. Measurements of such lesions may no longer be suitable for accurate assessment of response and/or progression. In this situation a sum of diameters including any residual lesion should still be calculated, and if the sum of diameters is still increased by 20% over nadir, disease progression is diagnosed. If doubt remains, the entire disease burden of the participant should be considered and compared with that at baseline as though there was only evaluable, non-measurable disease at baseline. In such a situation, non-CR/non-PD becomes a possible timepoint assessment and even best overall response even though there was measurable disease at baseline. To minimize the risk of this eventuality, study imaging before biopsy is advised.

- *Evaluation of Nontarget Lesions*

While some nontarget lesions may actually be measurable, they need not be measured (except lymph nodes when pathological nature is uncertain) and instead should be assessed only qualitatively, according to the timepoint assessment criteria shown in [Table 19](#) below:

Table 19 Response Status Definition for Nontarget Lesions at Each Timepoint

Observed disease	Response	Abbreviation
Disappearance of all nontarget lesions except for lymph nodes. All lymph nodes must be nonpathological in size (< 10 mm short axis)	Complete Response	CR
Persistence of 1 or more nontarget Lesions	Neither complete response nor progressive disease	Non-CR/non-PD
Unequivocal progression of existing nontarget lesions	Progressive disease	PD
No nontarget lesions seen at baseline	No nontarget lesions	NA
Assessment not possible due to inadequate or missing images	Not Evaluable	NE

- *Special points*

When the participant has both target and nontarget lesions. To achieve ‘unequivocal progression’ on the basis of the nontarget disease, there must be an overall substantial worsening in nontarget disease such that, even in the presence of SD or PR in target disease, the overall tumor burden has increased sufficiently to merit new therapy. A modest ‘increase’ in the size of 1 or more nontarget lesions is insufficient to qualify for unequivocal progression status. The designation of overall progression solely on the basis of change in nontarget disease in the face of SD or PR of target disease will therefore be extremely rare.

When the participant has only nontarget lesions. In this study, it is not a requirement for study entry to have measurable disease. The same general concepts apply here as noted above; however, in this instance there will be no measured disease assessment to balance the interpretation of an increase in non-measurable disease burden. The test that should be applied when assessing participants for unequivocal progression is to consider if the increase in overall disease burden based on the change in non-measurable disease is at least comparable in magnitude to the increase that would be required to declare PD for measurable disease.

- *Evaluation of New Lesions*

The appearance of new malignant lesions denotes disease progression by RECIST v1.1. The finding of a new lesion should be unequivocal: i.e. not attributable to differences in scanning technique, change in imaging modality, or findings thought to represent something other than tumor. A lesion identified on a follow-up study in an anatomical location that was not scanned at baseline is considered a new lesion and will indicate PD. Exceptionally, since the endpoints of this study differentiate between locoregional progression and distant metastasis, it is necessary to differentiate between locoregional lesions and metastases elsewhere. Therefore, data on new lesions in each of these *locations* will be required if available. If the first manifestation of disease progression is distant metastasis, then assessments for locoregional control should continue if possible, and vice versa. Note: As this study is in locally advanced disease, all target and nontarget lesions at baseline will lie within the locoregional volume and therefore no similar differentiation at baseline is possible or required.

If a new lesion is equivocal, either continued therapy and follow-up evaluation or biopsy and histological examination will clarify if it represents truly new disease. If repeat scans or biopsy confirm a new lesion, then PD should be declared using the date of the initial scan.

In case histopathological results of a new lesion unequivocally reveal a non squamous histology of the new malignant lesion, this will not be counted as disease progression within the secondary endpoints of this study.

Evaluation of Disease Status at Each Postbaseline Timepoint

For participants with measurable disease, the assessment of response status at each timepoint will be an *amalgamation* of the individual response statuses of target lesions, nontarget lesions and new lesions, and is shown in [Table 20](#) below.

Table 20 Timepoint Assessment of Disease Status by Imaging for Participants With Measurable Disease at Baseline.

Timepoint Response in:			Overall Timepoint Response
Target Lesions	Nontarget Lesions	New Lesions	
CR	CR	No	CR
CR	Non-CR/non-PD	No	PR
CR	NE	No	PR
PR	Any, except PD, or NE	No	PR
SD	Any, except PD, or NE	No	SD
Not all measured	Any, except PD	No	NE
PD	Any	Yes or no	PD
Any	PD	Yes or no	PD
Any	Any	Yes	PD

CR=complete response, NE=not evaluable, PD=progressive disease, PR=partial response, SD=stable disease.

The RECIST papers referenced in this document provide no similar assessment paradigm for response status at timepoint for participants with evaluable but non-measurable disease at baseline, but one can be derived from the information above, and it is provided in [Table 21](#) below.

Table 21 Timepoint Assessment of Disease Status by Imaging for Participants With Non-measurable Disease at Baseline, or due to Biopsy or Excision

Timepoint Response		Overall Timepoint Response
Nontarget Lesions	New Lesions	
CR	No	CR
Non-CR/non-PD	No	Non-CR/non-PD
NE	No	NE
PD	Yes or no	PD
Any	Yes	PD

CR=complete response, NE=not evaluable, PD=progressive disease.

- *Special points*

Impact of biopsy and excision. Due to biopsy or excision of target lesions, some participants with measurable disease at baseline may have a timepoint response or best overall response of Non-CR/Non-PD

Symptomatic progression. Symptomatic progression alone is not a determinant of disease progression in this study.

Handling equivocal findings of progression. For equivocal findings of progression (e.g. very small and uncertain new lesions; cystic changes or necrosis in existing lesions), in the absence of histological verification of new malignant lesions, treatment may continue at the investigator's discretion until the next scheduled assessment. If, at the next scheduled assessment, progression is definite, the date of progression should be the earlier date when progression was first suspected

Further Information

Further information on the assessment of disease by imaging in this study is available in the training materials, including slide presentations and/ or videos.

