8.1 Efficacy Assessments and Procedures

Assessment of tumor response to treatment will be assessed locally according to the Response Evaluation Criteria in Solid Tumors (RECIST v1.1) as described in [Appendix 2](#) but will also take into consideration clinical, anatomopathological, and functional assessments of the tumor.

Tumor assessments (clinical and radiological) should be continued until disease progression (as per RECIST v1.1) occurs, next line of anticancer treatment is started, or EOS, whichever occurs first as per SoAs ([Table 1](#), [Table 2](#), and

[Table 3](#)) and are scheduled, after the EOT visit, every 3 months.

Participants who progress (as per RECIST v1.1) or who start next line of anticancer treatment will discontinue the study. If study intervention is permanently discontinued in participants without disease progression according to RECIST v1.1 (e.g. unacceptable toxicity), the participant will remain in the study to be evaluated for safety and efficacy. The SoA indicates data to be collected at the time of discontinuation of study intervention and follow-up and for any further evaluations that need to be completed (

[Table 3](#)-EOT visit). Efficacy assessments will continue to be performed until disease progression, start of next line therapy, or EOS, whichever occurs first.

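### Appendix 2's progression rule for biopsied or excised target lesions omits the 5 mm absolute increase that Table 18 requires, so the two disagree when the nadir sum is below 25 mm

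*Protocol*

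**What the plan says.** Protocol Appendix 2, Table 18, defines progressive disease in target lesions by two conditions that must both hold. The relative one is "At least a 20% increase in the sum of diameters of target lesions, taking as reference the smallest sum on study or at baseline". The absolute one follows at once: "In addition to the relative increase of 20%, the sum must also demonstrate an absolute increase of at least 5 mm".

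Below Table 18, the special point on target lesions that have been biopsied or excised first warns that "Measurements of such lesions may no longer be suitable for accurate assessment of response and/or progression". It still asks for a sum of diameters that includes any residual lesion, and then says that "if the sum of diameters is still increased by 20% over nadir, disease progression is diagnosed". It does not mention 5 mm and does not refer back to Table 18. The next sentence gives a way out: "If doubt remains, the entire disease burden of the participant should be considered and compared with that at baseline", as if the participant had only had non-measurable disease. In that case an outcome of neither complete response nor progression becomes possible.

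On the consequence, protocol Section 8.1 says: "Participants who progress (as per RECIST v1.1) or who start next line of anticancer treatment will discontinue the study". Section 9.4.1 defines PFS by first documented progression or death, and LRC by first progression at the primary site or the locoregional nodes.

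**The concern.** Appendix 2 gives two numerical thresholds for the same decision. The lower one applies to lesions whose measurement the plan itself regards as doubtful, and no reason is given for lowering it there. Response is assessed locally by investigators (Section 8.1), so one site may treat the special point as an exception to Table 18 while another treats it as shorthand for Table 18. Two participants with the same measurements could then be classified differently because of a biopsy or because of the site.

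Appendix 2 notes that all baseline target lesions lie within the locoregional volume. Progression called on the target-lesion sum can therefore enter both PFS and LRC, and under Section 8.1 it can end follow-up, after which no later assessment could correct the call.

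**Working it through.** Neither document derives a figure on this point, so there is none to reproduce. The check compares the two stated rules.

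**Inputs.** Special point for biopsied or excised lesions: 20% over nadir. Table 18: at least 20% over nadir and at least 5 mm. Appendix 2 default for a residual lesion that is only faintly visible and cannot be measured: 5 mm.

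**Formulas.** Let N be the nadir sum in mm.
- Rise needed under the special point = 0.20 × N
- Rise needed under Table 18 = max(0.20 × N, 5)
- The rules differ when 0.20 × N < 5, that is, when N < 5/0.20 = 25 mm

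| Nadir sum (mm) | Special point (mm) | Table 18 (mm) | Table 18 rise as % of nadir |
|---|---|---|---|
| 5 | 1.0 | 5.0 | 100.0 |
| 10 | 2.0 | 5.0 | 50.0 |
| 15 | 3.0 | 5.0 | 33.3 |
| 20 | 4.0 | 5.0 | 25.0 |
| 24 | 4.8 | 5.0 | 20.8 |
| 25 | 5.0 | 5.0 | 20.0 |
| 30 | 6.0 | 6.0 | 20.0 |

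A rise of 1 to 3 mm is enough under the special point only for nadir sums of 5 to 15 mm. Between 15 and 25 mm the rise needed is 3 to just under 5 mm. At 25 mm or more the 5 mm condition is met automatically and nothing changes.

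**An example from the plan's own conventions.** A single residual lesion is carried at the default 5 mm and later measured at 6 mm. The rise is 1/5 = 20%. That is progression under the special point and not under Table 18, which would need 10 mm.

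**Can small sums occur?** Yes. Appendix 2 has target nodes recorded even after they shrink below 10 mm, and it provides the 5 mm default. The documents give no distribution of nadir sums and no rate of biopsy or excision of target lesions, so the number of participants affected cannot be calculated.

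**The case against.** The best defence is that there is only one rule. Appendix 2 introduces Table 18 by saying that "the details of the outcome of each comparison are shown in [Table 18](#) below", and the special point sits beneath that table. On this reading the 20% is shorthand for the full criterion, and the sentence serves only to say that a sum must still be calculated. That reading is possible but not compelled: a specific rule placed after a general one can equally be taken as an exception to it.

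The second defence is the clause for remaining doubt, and part of it stands. A reader might infer that this clause never restores the 5 mm condition. The documents do not support that. It moves the participant to the non-measurable assessment, for which Appendix 2 asks for an increase comparable in size to the one that would be progression in measurable disease. The comparison is also with baseline rather than nadir. But the route depends on the assessor's doubt, and the measurable-disease threshold it leads back to is the one left ambiguous.

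Four other stronger inferences are tempting.
- **Study exit is automatic.** Section 8.1 supports exit on RECIST progression, but Section 1.3 speaks of confirmed progression, and Appendix 2 allows equivocal findings to wait for the next scheduled assessment.
- **Remaining study intervention is stopped.** Table 2 schedules no CT or MRI in the combination period. Table 3 places imaging at EOT (Week 20) and every 3 months afterwards, beyond the 18-week treatment period. Only unscheduled imaging during treatment could have this effect.
- **Biopsy of target lesions is common.** The special point presents it as occasional. Section 8.1.1 asks for biopsy when residual disease at the primary site is suspected at EOT, where possible. Such a biopsy also yields histology that bears on the call.
- **A false-progression rate can be attached.** Assume no true growth, a 10 mm nadir and a per-scan error SD of 1, 1.5 or 2 mm. Then P(Z > threshold/(SD × √2)) is 7.9%, 17.3% or 24.0% for a 2 mm threshold, against less than 0.1%, 0.9% or 3.9% for 5 mm. These values show the direction of the effect. They are not a trial-level rate: the SDs and the nadir are assumptions, and the calculation is conditional on a biopsied target lesion with no doubt invoked.

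**Conclusion.** The inconsistency is real and confined to nadir sums below 25 mm. Within that range, a literal reading of the special point allows progression on a smaller rise than Table 18 does: +2 mm against +5 mm at a 10 mm nadir. It does so for lesions whose measurement the same paragraph questions. The result can be a PFS and LRC event and loss of further follow-up.

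This conclusion rests on the literal reading and on the assessor not using the route for doubtful cases. The frequency is unknown.

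The reach is limited. PFS and LRC are secondary endpoints, and the primary endpoint of DLT-like events does not use RECIST. SAP version 2.0 (Sections 7.1 and 14) drops the efficacy analyses and keeps only a listing of efficacy results, so no planned PFS or LRC estimate would be distorted. What remains is individual classification in that listing and the follow-up of the participants concerned. It is still worth correcting, because the text states a threshold that conflicts with the plan's own table.

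**What to change.** In Appendix 2, reword the special point on biopsied or excised target lesions so that progression is diagnosed when the recalculated sum, including any residual lesion, meets the Table 18 criterion for progressive disease: at least 20% and at least 5 mm over nadir. If the omission was deliberate, say so and give the reason. Align the imaging training materials mentioned at the end of Appendix 2.

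The cost is one sentence and a check of the training materials. No new data, assessments or analyses are needed.
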